## 12.6 Data Analysis Plans

### 12.6.1 Analysis Plans for Primary Objective

All subjects with measurable disease who have received at least one cycle of treatment and have their disease re-evaluated will be evaluable for assessment of objective response. The objective response rates as determined by RECIST 1.1 and their associated 95% confidence intervals will be constructed based on the exact binomial test.

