- 7: Urinalysis for bilirubin, blood, glucose, ketones, pH, protein, specific gravity to be performed at screening and as clinically indicated throughout the study per site investigator's discretion.
- 8: Radiology imaging to include: CT of the chest, CT or MRI of the abdomen/pelvis and bone scan (in subjects with bone metastasis). Scans should be performed at screening then every 2 months ( $\pm$  7 days) during Cycles 1-7 (e.g., after C2, C4, etc.) and then every 3 months ( $\pm$  7 days) until the time of progression. Imaging for the D30 safety visit may be omitted if already performed within 2 past months.
- 9: Tremelimumab will be given approximately every month for up to 7 cycles in the absence of disease progression or prohibitive toxicity. Refer to Section 5 for information regarding monitoring of subjects during infusion.

10: Representative formalin-fixed paraffin-embedded (FFPE) tumor specimens in paraffin blocks (blocks preferred) or at least 15 unstained slides will be identified prior to subject registration and shipped prior to C1D1. If archival tissue is not available and the subject is undergoing a standard of care biopsy, tissue from the biopsy is required to be submitted for correlative analyses. Subjects without adequate baseline tumor tissue may be considered for enrollment on a case by case basis after discussion with the sponsor-investigator. See Correlative Laboratory Manual (CLM) for additional details.

11: Surplus tissue remaining after routine standard of care procedures (e.g., metastatic biopsies) during and after treatment will be collected during this study. Subjects may have tumor tissue obtained during the course of the study or at the time of disease progression for clinical purposes (e.g., confirmation of disease progression, management of complication of disease progression, etc.). Subjects will have the option of whether samples obtained during standard of care procedures may be used for research purposes. Samples for correlative analysis are required if a standard of care biopsy is performed at screening for the first 7 cycles of treatment. See CLM for additional details.

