### 9.3 Evaluation of best overall response

The best overall response is the best response recorded from the start of the treatment until disease progression/recurrence (taking as reference for PD the smallest measurements recorded since the treatment started). In general, the subject's best response assignment will depend on the achievement of both measurement and confirmation criteria.

| Target Lesions | Non-Target lesion             | New Lesion | Overall response |
|----------------|-------------------------------|------------|------------------|
| CR             | CR                            | No         | CR               |
| CR             | Non-CR/ Non-PD                | No         | PR               |
|                | Not evaluated                 | No         | PR               |
| PR             | Non-CR/ Non-PD/ not evaluated | No         | PR               |
| SD             | Non-CR/ Non-PD/ not evaluated | No         | SD               |
| PD             | Any                           | Yes or No  | PD               |
| Any            | PD*                           | Yes or No  | PD               |
| Any            | Any                           | Yes        | PD               |

\*In exceptional circumstances, unequivocal progression in non-target lesions may be accepted as disease progression.

Subjects with a global deterioration of health status requiring discontinuation of treatment without objective evidence of disease progression at that time should be classified as having “symptomatic deterioration”. Every effort should be made to document the objective progression even after discontinuation of treatment. In some circumstances it may be difficult to

distinguish residual disease from normal tissue. When the evaluation of complete response depends on this determination, it is recommended that the residual lesion be investigated (fine needle aspirate/biopsy) to confirm the complete response status.

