### **9.4.2 Confirmation of Response**

To be assigned a status of complete or partial response, changes in tumor measurements must be confirmed by repeat assessments performed no less than four weeks after the criteria for response are first met.

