### **9.4.5 Objective response rate**

The objective response rate is the proportion of all subjects with confirmed PR or CR according to RECIST, from the start of treatment until disease progression/recurrence (taking as reference for progressive disease the smallest measurements recorded since the start of treatment).

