### 12.3 Sample Size and Accrual

A Simon's 2-stage design will be applied. Patients who do not receive drug or who do not complete 1 cycle of therapy for non-treatment related causes (eg, traffic accidents, trauma etc) will be replaced.

The null hypothesis that the true response rate is 2% will be tested against a one-sided alternative. In the first stage, 18 subjects will be accrued. If there are 0 responses in these 18 subjects, enrollment will be stopped. Otherwise, 10 additional subjects will be accrued for a total of 28. The null hypothesis will be rejected if 3 or more responses are observed in 28 subjects. This design yields a type I error rate of 0.02 and power of 80% when the true response rate is 15% or larger.

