### 12.4 Assessment of Safety

The safety population will be defined as any patients that receive at least one dose of tremelimumab and will be used in the assessment of toxicity. Safety will be determined according to the NCI Common Terminology Criteria for Adverse Events (NCI CTCAE) v4.03. All subjects will be evaluable for adverse event evaluation from the time of their first dose of study treatment.

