### 12.5 Assessment of Efficacy

All subjects who have received at least one cycle of therapy and have had their disease re-evaluated will be considered evaluable for response (exceptions will be those who exhibit objective disease progression prior to the end of Cycle 1 who will also be considered evaluable).

Patients who do not receive drug or who do not complete 1 cycle of therapy for non-treatment related causes will be replaced.

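### The primary ORR leaves dosed but never re-assessed subjects out of its denominator, contrary to Section 9.4.5; any such subject biases the reported rate and its exact CI upward

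*Combined protocol and SAP*

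**What the plan says.** Three places in the combined protocol and SAP bear on the denominator of the primary endpoint.

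- Section 9.4.5: "The objective response rate is the proportion of all subjects with confirmed PR or CR according to RECIST".
- Section 12.5: "All subjects who have received at least one cycle of therapy and have had their disease re-evaluated will be considered evaluable for response". It adds one exception, for subjects with objective progression before Cycle 1 ends.
- Section 12.6.1, the primary analysis plan, requires measurable disease and covers those "who have received at least one cycle of treatment and have their disease re-evaluated will be evaluable for assessment of objective response", with a 95% exact binomial interval. It does not repeat the exception, although a subject with objective progression has been assessed and may already fall inside its wording.

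Other sections decide who can be lost. Section 9.4.2 says that the tumor changes behind a response "must be confirmed by repeat assessments performed no less than four weeks after the criteria for response are first met". Study calendar footnote 8 says "Scans should be performed at screening then every 2 months", so the first on-treatment scan follows Cycle 2. Section 9.3 foresees "Subjects with a global deterioration of health status requiring discontinuation of treatment without objective evidence of disease progression at that time". Replacement (Sections 5, 12.3 and 12.5) covers only subjects who get no drug or who fail to complete Cycle 1 for reasons unrelated to treatment. By contrast, the safety population in Section 12.4 is "any patients that receive at least one dose of tremelimumab".

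**The concern.** The primary objective is to estimate the ORR, so the denominator is part of the estimand. Under 12.5 and 12.6.1, a dosed subject with no post-baseline assessment is removed rather than counted as a failure. Confirmation needs a repeat assessment, so that subject could never have entered the numerator. The exclusion is therefore not neutral: it removes only certain non-responders.

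This kind of loss is foreseeable in a population that has already progressed on PD-1/PD-L1 therapy, with about two months to the first scan. At stake are the reported point estimate and interval, and comparability with the safety results, which use all dosed subjects.

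A second, smaller question is what the planned counts mean. Section 12.3 says "In the first stage, 18 subjects will be accrued" and 28 in total, without stating whether these are dosed or evaluable subjects.

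**Working it through.** **Inputs.** From Section 12.3: null rate 2%, alternative 15%, 18 subjects in stage 1 (stop at 0 responses), 10 more in stage 2, reject at 3 or more of 28; stated type I error 0.02 and power 80%. From Section 12.6.1: exact 95% interval. The number of dosed subjects without an assessment is not in the documents. I assume 1, 3 or 6 of 28 for the estimate and 5 to 20% for the error rate.

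**Step 1: reproduce the design.** With X1 ~ Bin(18, p) and X2 ~ Bin(10, p),

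P(reject) = P(X1=1)·P(X2≥2) + P(X1=2)·P(X2≥1) + P(X1≥3).

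- p = 0.02: 0.0041 + 0.0081 + 0.0052 = 0.0174, which is 0.02 at the two decimals stated.
- p = 0.15: 0.0777 + 0.2053 + 0.5203 = 0.8033.

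The plan's figures hold.

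**Step 2: direction of the bias.** Let x responders arise among n dosed subjects, of whom m have no post-baseline assessment. The all-dosed ORR is x/n. The ORR under 12.6.1 is x/(n−m), because none of the m can be in x. The ratio is n/(n−m), which exceeds 1 whenever m ≥ 1. If x = 0 or m = 0, the two estimates coincide.

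**Step 3: size.** Exact limits are the 2.5% quantile of Beta(x, n−x+1) and the 97.5% quantile of Beta(x+1, n−x), with n the denominator used. Take x = 3, the smallest count that rejects the null, and 28 dosed:

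| Unassessed (assumed) | Reported ORR | Exact 95% CI | Ratio to 3/28 |
|---|---|---|---|
| 0 | 3/28 = 10.7% | 2.3–28.2 | 1 |
| 1 | 3/27 = 11.1% | 2.4–29.2 | 28/27 = 1.04 |
| 3 | 3/25 = 12.0% | 2.5–31.2 | 28/25 = 1.12 |
| 6 | 3/22 = 13.6% | 2.9–34.9 | 28/22 = 1.27 |

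Both limits rise in every row.

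**Step 4: the decision rule.** If 28 counts dosed subjects, the rule is still 3 or more responders among those 28, and the type I error stays at 0.0174. If 18 and 28 are instead filled with evaluable subjects only, and a fraction d of dosed subjects is unassessed, an all-dosed rate of 2% appears as 0.02/(1−d) among evaluable subjects. Putting that into the Step 1 formula:

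| d (assumed) | Rate among evaluable | P(reject) |
|---|---|---|
| 5% | 0.0211 | 0.020 |
| 10% | 0.0222 | 0.023 |
| 15% | 0.0235 | 0.027 |
| 20% | 0.0250 | 0.031 |

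On this reading about 28/(1−d) subjects would be dosed on average: 29.5 at 5% and 35 at 20%.

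**The case against.** The strongest reply is that the plan does choose a set. Sections 12.5 and 12.6.1 agree on its core, 12.6.1 is the dedicated primary-analysis section, and 9.4.5 sits among general RECIST definitions and names no analysis set. Response-evaluable sets are also a recognised phase 2 choice. This has force. A reader might infer that two equal definitions compete and that the choice could be made after the data are seen. The documents do not go that far: although they contain no precedence clause, the ordinary reading is that 12.6.1 governs. But if 12.6.1 governs, the exclusion applies, so this reply does not remove the bias.

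A second reply is that losses may be few. Eligibility requires ECOG 0 or 1, life expectancy of at least 12 weeks, and no progression within 2 months of starting the earlier PD-1/PD-L1 therapy. Safety-visit imaging and the Section 9.3 request to document progression after stopping treatment will recover some subjects. That stands against the top of the assumed range. It does not help with subjects who die or withdraw before any scan, and the 12.5 exception requires objective progression.

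Third, the shift is small beside an interval of roughly 2 to 28%. That is correct.

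Fourth, the replacement rule might look like part of the fault. It is a deliberate rule, stated three times, for losses unrelated to treatment. Ending it for dosed subjects would be a separate design trade-off: if one dosed subject is lost as a certain non-responder and 15% applies to the rest, power falls from 80.3% to between 78.1 and 78.5%. Correcting the denominator does not require it.

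**Conclusion.** The point holds conditionally. The analysis set in 12.5 and 12.6.1 is narrower than the ORR defined in 9.4.5, and no all-treated ORR is planned. Given at least one dosed, unassessed subject and at least one responder, the reported ORR and both confidence limits are biased upward. If every dosed subject is assessed, there is no bias. With 3 responders and 28 dosed, the assumed losses of 1, 3 and 6 add about 0.4, 1.3 and 2.9 percentage points. These are illustrations, not predictions, since the documents give no non-evaluable rate.

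Two stronger conclusions are tempting. One is that the go/no-go decision is compromised. That does not follow if 28 counts dosed subjects. It becomes a modest excess over the stated 0.02 only if the counts are filled with evaluable subjects and 10% or more are unassessed. The other is that the bias matters because it can carry the estimate past 15%: for instance, 4/28 = 14.3% would be reported as 4/26 = 15.4%. But 15% is the alternative used for power, not a decision threshold, and no protocol conclusion changes when the estimate crosses it.

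The plan should be corrected because the repair is cheap and the ORR is what the trial sets out to estimate. The trial is not invalid without it.

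**What to change.** In Sections 12.5 and 12.6.1, define the primary ORR set as all subjects who receive at least one dose. This agrees with 9.4.5 and matches the safety population in 12.4. State that anyone without a confirmed CR or PR counts as a non-responder, including subjects with no post-baseline scan. Report the response-evaluable ORR, as defined in 12.5, as a sensitivity analysis.

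Leave the replacement rule as it is, and add that a subject who was dosed and then replaced stays in the reported all-dosed denominator. That denominator may then exceed 28: with one such subject, 3 responders give 3/29 = 10.3%.

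The cost is a few sentences in the protocol and a reported ORR that may be slightly lower. No change to the planned sample size or the decision rule is needed.

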## 2. STUDY OBJECTIVES AND ENDPOINTS

### 2.1 Objectives

#### 2.1.1 Primary Objective

Estimate the objective response rate (RECIST 1.1) with tremelimumab in subjects with metastatic urothelial cancer previously treated with PD-1/PD-L1 blockade

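### The planned exact binomial 95% interval for the response rate ignores the stop at 0/18, so its upper limit is slightly too low when responses are few

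*Combined protocol and SAP*

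**What the plan says.** Section 2.1.1 makes estimation the primary objective: "Estimate the objective response rate (RECIST 1.1) with tremelimumab". Section 12.3 sets a Simon two-stage design. Of the first stage it says "In the first stage, 18 subjects will be accrued" and then "If there are 0 responses in these 18 subjects, enrollment will be stopped"; if the trial goes on, "Otherwise, 10 additional subjects will be accrued for a total of 28". The decision rule is "The null hypothesis will be rejected if 3 or more responses are observed in 28 subjects", and the stated operating characteristics are "This design yields a type I error rate of 0.02 and power of 80% when the true response rate is 15% or larger".

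For the analysis of the primary endpoint, section 12.6.1 says "The objective response rates as determined by RECIST 1.1 and their associated 95% confidence intervals will be constructed based on the exact binomial test". Neither that section nor any other mentions an estimator or an interval that takes account of the first-stage stop.

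**The concern.** The type I error and power in 12.3 are computed under two-stage sampling, whereas the estimate and interval in 12.6.1 treat the data as one fixed sample. A result of x/28 can arise only if at least one response fell among the first 18, and some trials that would have reached one or two responses in 28 instead end at 0/18. The single-stage lower-tail probability leaves those trials out, so the upper limit it yields at a low count is too low.

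Because the primary objective is to estimate the response rate, the estimate and its interval are the main reported result. Section 12.1 adds that even a fairly low response proportion could matter clinically. Low counts are plausible: the chance of finishing with 1 or 2 of 28 is 29% at a true rate of 2%, 44% at 5%, 32% at 10% and 14% at 15%.

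**Working it through.** **Inputs.** From 12.3: n1 = 18, stop if there are 0 responses, n2 = 10, N = 28, reject at 3 or more, null 2%, target 15%. From 12.6.1: a 95% exact binomial interval, read here as Clopper-Pearson with 2.5% in each tail. Exactly 18 and 28 evaluable subjects are assumed. Let X be the stage 1 responses and Y the stage 2 responses.

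**1. The plan's own figures.** P(reject) = P(X ≥ 3) + P(X = 2)·P(Y ≥ 1) + P(X = 1)·P(Y ≥ 2).

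- At 2%: 0.0052 + 0.0443 × 0.1829 + 0.2554 × 0.0162 = 0.0174, which rounds to the stated 0.02.
- At 15%: 0.5203 + 0.2556 × 0.8031 + 0.1704 × 0.4557 = 0.8033, matching the stated 80%.

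The design figures are right.

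**2. Upper limit at 1/28.**

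- The planned limit solves (1−p)^28 + 28p(1−p)^27 = 0.025, giving p = 18.35%.
- Under the actual design the results as low or lower are a stop at 0/18, or one response in stage 1 and none in stage 2. The limit solves (1−p)^18 + 18p(1−p)^27 = 0.025, giving p = 20.27%.
- Check at 18.35%: 0.0260 + 0.0139 = 0.0399, not 0.025. At 20.27%: 0.0170 + 0.0081 ≈ 0.025.

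**3. All low counts.** Results are ordered 0/18 lowest, then 1/28, 2/28 and so on, and each 2.5% tail is inverted.

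| Result | Observed | Planned 95% CI | Two-stage 95% CI | UMVUE |
|---|---|---|---|---|
| 0/18 | 0% | 0 to 18.53% | 0 to 18.53% | 0% |
| 1/28 | 3.6% | 0.09 to 18.35% | 0.14 to 20.27% | 5.6% |
| 2/28 | 7.1% | 0.88 to 23.50% | 0.94 to 24.01% | 8.1% |
| 3/28 | 10.7% | 2.27 to 28.23% | 2.30 to 28.35% | 11.1% |
| 4/28 | 14.3% | 4.03 to 32.67% | 4.04 to 32.69% | 14.4% |
| 6/28 | 21.4% | 8.30 to 40.95% | 8.30 to 40.95% | 21.4% |

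The planned upper limit for 1/28 is below the one for 0/18. The two-stage interval removes that reversal. The planned lower limit errs slightly on the conservative side.

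**4. Coverage of the planned interval under two-stage sampling.** Just above 18.53%, the upper limits for both 0/18 and 1/28 lie below the truth. At p = 18.54% the upper-side miss is (1−p)^18 + 18p(1−p)^27 = 0.0249 + 0.0131 = 0.038, against a nominal maximum of 0.025. The lower-side miss is 0.0241, so coverage is 1 − 0.0381 − 0.0241 = 0.938. Above about 18.64%, the planned lower limit for 10/28, the lower-side misses drop and coverage recovers. Coverage is below 95% only between about 18.54% and 18.64%. It is 98.3% at 2%, 98.8% at 5%, 98.2% at 10%, 98.2% at 15% and 95.8% at 20%. The upper-side miss alone exceeds 2.5% over roughly 18.5 to 20.3% and 23.5 to 24.0%.

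**5. Bias of responses divided by subjects.** A stopped trial contributes zero, so the mean over the whole design is [18p + 10p(1 − (1−p)^18)]/28 and the bias is −(10/28)·p·(1−p)^18.

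- 2%: −0.357 × 0.02 × 0.695 = −0.50 point.
- 5%: −0.357 × 0.05 × 0.397 = −0.71 point, close to the largest value.
- 10%: −0.54 point. 15%: −0.29 point.

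Among trials that reach stage 2 the sign reverses: the mean of x/28 is 7.1% at a true 5% and 15.5% at a true 15%.

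**The case against.** The case for leaving 12.6.1 alone is that the effect is small and falls where it matters least. At 3/28, the lowest count that rejects the null, the upper limit moves by 0.12 point, and from 6/28 the limits agree to 0.01 point. The visible shift is at 1/28, where the trial has already failed; that result has probability 3.4% at a true rate of 15%. Apart from a window about 0.1 point wide, the planned interval covers at least 95%. The observed proportion is transparent, and its bias of at most 0.7 point is small beside a standard error of about 7 points at 15%. All of this stands, and it limits the weight of the point.

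Replacing x/n with the UMVUE would also be a trade-off. At a true 2% its root mean squared error is 3.2 points against 2.6 for x/n, and among trials that continue it is further above the truth (8.3% at a true 5%, 15.9% at a true 15%). That stands too, and is why the UMVUE belongs in a supplementary line.

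One might add that two-stage intervals depend on how outcomes are ordered. Here that carries little force: the only early stop is at zero responses, and stage-wise and UMVUE orderings both place 0/18 lowest.

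A reader might also infer that at 1/28 the method decides whether this trial is compatible with the 18.8% response rate cited in section 1.2.2, since 18.35% excludes it and 20.27% does not. The documents plan no such comparison, and the cited figure comes from 32 patients with its own interval of 7.2 to 36.4%.

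**Conclusion.** The point holds for the interval. A single-stage exact interval is planned for two-stage data; its upper limit is too low by 1.92 points at 1/28, 0.51 at 2/28 and 0.12 at 3/28, it puts 1/28 below 0/18, and it does not guarantee 95% coverage (minimum 93.8%). The correction is worth making because it concerns the main reported result and costs almost nothing.

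Two stronger readings are not supported. One is that coverage fails across the range between the 2% null and the 15% target: it is about 98% or more at 2%, 5%, 10% and 15%. The other is that the reported estimate is simply biased low: that is true only when averaged over the whole design, by at most 0.7 point, and is reversed among trials that continue. Nor is the test affected, because the error rates in 12.3 already reflect the two stages.

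The figures assume exactly 18 and 28 evaluable subjects. The synopsis gives the total as approximate, and 12.5 and 12.6.1 restrict evaluability and allow replacement, so other attained sizes would shift the limits.

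**What to change.** In 12.6.1, state that the 95% confidence interval for the objective response rate will be an exact interval on the two-stage sample space, with 0/18 ordered lowest, then 1/28, 2/28 and so on, computed with the stage sizes actually attained. Keep the observed proportion as the reported rate and give the UMVUE alongside it as a supplementary estimate.

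The cost is one sentence, a short calculation with standard software, and a slightly wider interval at one or two responses. Naming the method now also removes any choice between intervals after the count is known. No extra subjects or data are needed.
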